7.3.1. Primary Endpoint

The primary endpoint is time to clinical response (TTCR) ([Table 5](#)).

Clinical response is defined as resolution of at least 4 of the 5 signs described below within the respective resolution criteria, maintained for at least 24 hours, or hospital discharge, whichever comes first.

Table 5 Criteria for Time to Clinical Response

Sign of clinical response	Response criteria
Hospital discharge	Subjects who are discharged from hospital will be considered to have met the clinical response endpoint at the time of hospital discharge and are not required to have documented resolution of at least 4 response criteria (i.e. achieved success at the time of discharge if not observed prior to it).
OR	
Temperature ¹	≤36.6°C (≤97.9°F) – axilla, or ≤37.2°C (≤99°F) – oral, or ≤37.7°C (≤99.9°F) – rectal/core ⁵ , tympanic
AND	
Oxygen saturation ^{2,3}	≥95% (without supplemental oxygen)
AND 2 out of the following 3 criteria:	
Respiratory status	
 Return to pre-morbid oxygen requirement (subjects with chronic oxygen use), OR Need for supplemental oxygen (administered by any modality – ventilator, non-invasive ventilation, facemask, facemask, nasal canula, etc) to no need for supplemental oxygen, OR Respiratory rate ≤24/min (without supplemental oxygen)
Heart rate	≤100/min
Systolic blood pressure ⁴	≥90 mmHg

- Without the use of antipyretics within 8 hours
- A subject with a history of chronic hypoxia (without supplemental oxygen) will satisfy normalization criteria for oxygen saturation if the value (without supplemental oxygen) is ≤2% from subject's historical oxygen saturation baseline as recorded within 12 months prior to enrolment as documented in the subject's medical records.
- This requirement will be waived for subjects with a history of chronic supplemental oxygen requirement who have a baseline oxygen saturation <95% with supplemental oxygen, within 12 months prior to enrolment as documented in the subject's medical records.
- Without inotropic support administered within 2 hours.
- Core temperatures include measurements via a temporal artery thermometer, indwelling catheters and Swan Ganz catheters.

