2. SUMMARY OF KEY PROTOCOL INFORMATION

2.1. Changes to the Protocol Defined Statistical Analysis Plan

Given that the study has been terminated early and only 10 subjects have been enrolled, no formal hypothesis testing will be performed for the study. All analyses will be descriptive and not intended for making definitive conclusions. Only a selected set of originally planned analyses will be performed and all data will be listed.

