7.1.2. Planned Efficacy Statistical Analyses

The clinical response is defined as hospital discharge due to clinical improvement or meeting following vital signs/ventilation criteria.

Sign of clinical response	Response criteria
Temperature ¹	≤36.6°C (≤97.9°F) – axilla/temporal, or
	≤37.2°C (≤99°F) – oral, or
	≤37.7°C (≤99.9°F) – rectal/core ⁵ , tympanic
AND	
Oxygen saturation ^{2,3}	≥95% (without supplemental oxygen)
AND 2 out of the following	ng 3 criteria:
Respiratory status	For subjects with chronic hypoxia and supplemental oxygen use: return to pre-morbid oxygen requirement, OR
	For subject with supplemental oxygen use at study entry: need for supplemental oxygen (administered by any modality – ventilator, non-invasive ventilation, facemask, face-tent, nasal canula, etc) to no need for supplemental oxygen, OR
	• For subject without supplemental oxygen use and respiratory rate > 24/min at study entry: respiratory rate ≤24/min
Heart rate	≤100/min
Systolic blood pressure ⁴	≥90 mmHg

- 1. Without the use of antipyretics within 8 hours
- 2. A subject with a history of chronic hypoxia (without supplemental oxygen) will satisfy normalization criteria for oxygen saturation if the value (without supplemental oxygen) is ≤2% from subject's historical oxygen saturation baseline as recorded within 12 months prior to enrolment as documented in the subject's medical records.
- 3. This requirement will be waived for subjects with a history of chronic supplemental oxygen requirement who have a baseline oxygen saturation <95% with supplemental oxygen, within 12 months prior to enrolment as documented in the subject's medical records.
- 4. Without inotropic support administered within 2 hours.
- 5. Core temperatures include rectal, indwelling catheters and Swan Ganz catheters.

Statistical Analyses

Endpoint(s)

• Time to Clinical Response (TTCR), days.

Derivation of TTCR

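### The SAP moves temporal-artery temperatures from the protocol's core limit (37.7 °C) to the axillary limit (36.6 °C) without declaring it, which can delay or remove primary-endpoint events in an unknown number of subjects, possibly none

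*SAP*

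**What the plan says.** Protocol 7.3.1, Table 5, sets the temperature limit by measurement route. The lowest limit is for axillary readings only: "≤36.6°C (≤97.9°F) – axilla, or". Oral readings have 37.2 °C. The highest limit is "≤37.7°C (≤99.9°F) – rectal/core", in a row shared with tympanic readings. Note 5 to that row defines core: "Core temperatures include measurements via a temporal artery thermometer, indwelling catheters and Swan Ganz catheters". A temporal-artery reading therefore falls under 37.7 °C.

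SAP 7.1.2 repeats the table with the same three limits but two edits. The lowest row now reads "≤36.6°C (≤97.9°F) – axilla/temporal, or", and note 5 becomes "Core temperatures include rectal, indwelling catheters and Swan Ganz catheters". Temporal has left the core definition and joined the axillary row. Rectal has been added to the note, which changes nothing because rectal was already in the 37.7 °C row.

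SAP 2.1 is the section for changes to the protocol-defined analysis. It says: "Given that the study has been terminated early and only 10 subjects have been enrolled, no formal hypothesis testing will be performed for the study". It adds that the analyses are descriptive and that "Only a selected set of originally planned analyses will be performed and all data will be listed". It says nothing about a response threshold. The further TTCR rules in SAP 11.6.4 do not mention it either.

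**The concern.** Temperature is compulsory in both tables. It is joined by AND to oxygen saturation and to two of the three remaining signs, so no other sign can stand in for it. Changing the limit for one route therefore changes what counts as a vital-sign response for subjects measured that way.

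A reader who relies on SAP 2.1 would take TTCR as reported to be the endpoint the protocol defined. For a subject with temporal readings between the two limits it may not be. SAP 7.1.2 plans no sensitivity analysis, so no planned output is specified that would show the result under the protocol limit.

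**Working it through.** **Inputs.** Limits and the core definition: Protocol Table 5 with note 5, and the response table in SAP 7.1.2 with note 5. Confirmation and censoring rules: SAP 7.1.2 and 11.6.4. Assessment frequency: Protocol 7.3.3. Number enrolled and allocation: SAP synopsis.

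**Step 1: check the limits.** With F = C × 9/5 + 32, 36.6 °C gives 97.88, 37.2 °C gives 98.96 and 37.7 °C gives 99.86. These round to the printed 97.9, 99 and 99.9 °F, so a misprinted limit does not explain the difference.

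**Step 2: compare by route.**

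| Route | Protocol limit | SAP limit | Change |
|---|---|---|---|
| Axilla | 36.6 °C | 36.6 °C | none |
| Oral | 37.2 °C | 37.2 °C | none |
| Rectal, indwelling or Swan Ganz catheter, tympanic | 37.7 °C | 37.7 °C | none |
| Temporal artery | 37.7 °C | 36.6 °C | 1.1 °C stricter |

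37.7 − 36.6 = 1.1 °C; on the printed Fahrenheit values, 99.9 − 97.9 = 2.0 °F.

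**Step 3: direction.** Any temporal reading at or below 36.6 °C is also at or below 37.7 °C. Every run of assessments that qualifies under the SAP limit therefore qualifies under the protocol limit, and the reverse fails for readings above 36.6 and up to 37.7 °C. With all other SAP rules held fixed, the SAP limit can leave an event where it is, make it later or remove it. It cannot make it earlier.

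**Step 4: follow the TTCR rules.** Vital signs are taken three times a day in hospital. To confirm a vital-sign response, SAP 7.1.2 requires every assessment within 22 hours of its onset, and at least one at or after 22 hours, to meet the criteria. Discharge due to clinical improvement can replace that confirmation, and the event is then dated to the onset of the vital-sign response. The cases are:

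- No temporal readings: no change.
- Another required sign is the last to normalise, and temporal readings are at or below 36.6 °C from then on: no change.
- Other signs normal, temporal readings between the limits, later falling to 36.6 °C or below and holding: a vital-sign event, but later.
- Readings stay between the limits until discharge due to clinical improvement: the event is dated to discharge instead of the earlier onset.
- Readings stay between the limits and there is no qualifying discharge: censored at the last vital-sign assessment. If the subject dies first, TTCR is set to 99 days, whereas SAP 11.6.4 does not count a death after response as a failure.

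**Step 5: how many subjects.** The documents do not give the routes used. With 10 enrolled, the number affected lies between 0 and 10. Arm sizes are not given either. Assuming 2:2:1 held exactly, 10 × 2/5 = 4, 10 × 2/5 = 4 and 10 × 1/5 = 2, before any exclusions from the influenza-positive population. In groups of that size, one moved event can change a Kaplan-Meier median or a response proportion.

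**The case against.** The best reply is that this is a gap in documentation. The SAP limit is printed openly in the primary-endpoint table, the analysis is descriptive with no hypothesis tested, and the SAP synopsis says that decisions on the final analysis are made before unblinding. The change may affect nobody. The planned TTCR and vital-sign listings and the individual TTCR plot might already let a reader see what happened.

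Much of this stands. No type I error or power figure is touched, and nothing in the documents suggests that the limit was chosen with knowledge of treatment. But the SAP still reports medians with confidence intervals and response proportions for the primary endpoint. The listing specifications do not name measurement route, and the mock shells are in a separate document, so whether route will appear cannot be checked.

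Three stronger readings are tempting and are not supported:

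- A reader might infer that every subject with temporal readings between the limits loses the vital-sign response and counts only at discharge. SAP 7.1.2 still allows a later confirmed response, and temperature may not be the sign that decides the timing.
- A reader might infer that the SAP makes TTCR depend on the thermometer for the first time. The protocol already has three route-specific limits; the SAP moves one route between two of them.
- A reader might infer that the SAP limit is wrong. Neither document gives a rationale for either classification, so that cannot be settled from the text.

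**Conclusion.** The two documents contradict each other on a compulsory component of the primary endpoint, and SAP 2.1 does not declare it. The size is 1.1 °C for temporal-artery readings and zero for every other route. The effect on a subject's TTCR runs one way: unchanged, later, moved to discharge, censored, or set to the death value.

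The effect on the results cannot be computed, because it depends on how many of the 10 subjects had temporal readings between the limits while temperature was the deciding sign. That number may be zero. The statement about small arms rests on the assumed 4, 4 and 2 split. One further limit: the SAP says it is based on the original protocol of 12 July 2016, and the protocol copy at hand has no title page, so the version match cannot be confirmed. No amendment in the documents explains the difference.

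**What to change.** Before unblinding, reconcile Protocol Table 5 with the response table in SAP 7.1.2.

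- If the SAP classification is kept, state the change and its reason in SAP 2.1.
- If no reason is given, derive primary TTCR with the classification the protocol pre-specified, and restore temporal-artery readings to note 5 in the SAP.
- In either case, show the temperature measurement route in the TTCR and vital-sign listings (31 and 33 in SAP Appendix 13), and flag any subject whose TTCR differs between the two limits. This needs no extra summary table.

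The cost is SAP wording, a second TTCR derivation for at most 10 subjects, and a listing column. The choice of limit on clinical grounds is for the sponsor.

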Table 4 Time and Events Table: Post-Treatment and Post-Discharge Assessments

Procedures	Post-Discharge Visits/TCs and Assessments Outpatient ^a					
	PT Day 3 (Visit)	Study Day 8 (TC)	Study Day 15 (TC)	Study Day 22 (TC)	Study Day 30 (TC)	Study Day 45 (Visit)
Safety/Efficacy Assessments						
Adverse events	X	X	X	X	X	X
Concomitant medications	X	X	X	X	X	X
Brief Physical Exam	X					X
Complications of influenza / associated antibiotic use ^b	X	X	X	X	X	X
Temperature	X	X	X	X	X	X
Other Vital signs (HR, BP, respiratory rate, oxygen saturation, ventilation status) ^c	X					X
Flu PRO ^d	Daily through Day 14	Daily through Day 14	X	X	X	X
Katz Activities of Daily Living ^e	X	X	X	X	X	X
Activity level ^f	Daily through Day 14	Daily through Day 14	X	X	X	X
Laboratory Assessments						
Clinical chemistry including LFTs ^g (Local+Central)	X					X
Serum Creatinine ^h (Local+Central)	X					X
Hematology ⁱ (Local+Central)	X					X
Pregnancy test ^j	X					
Nasopharyngeal swabs	X					
Exploratory Biomarkers (Blood Sample) ^k	X					X
Transcriptomics (blood sample) ^l	X					X
Nasal SAM strips (biomarkers) ^m	X					X
Nasal washes ⁿ	X					X
Hospital Readmission Status	X	X	X	X	X	X

a. Following discharge from hospital, outpatient clinic visit/TC schedule of assessments will be followed for those patients who are discharged before Day 45. For 5 days treatment, PT Day 3 will be the same as Day 8 and will be a clinic visit.

- b. Complications of influenza such as bacterial pneumonia, pneumothorax, pleural effusion, ARDS, myositis, encephalitis, myocarditis, and associated antibiotic use will be recorded on all assessment days.
- c. Vital signs and ventilation status will be assessed at clinic visits (PT Day 3 and Day 45).
- d. FLU PRO to be measured once daily through Study Day 14.
- e. Activities of Daily Living (Katz Scale) to be done at clinic visits and at TCs.
- f. Activity level assessed by reporting on a 3 point scale of bed rest (1), limited ambulation (2) or unrestricted (3) to be done daily through Study Day 14.
- g. Clinical chemistry including LFTs to be required once every other day until PT Day 3 (for LFTs, local testing for subject management until PT Day 3; central testing for all assessments, including at Day 45).
- h. Serum creatinine required once every day until PT Day 3 (local testing for subject management until PT Day 3; central testing for all assessments, including at Day 45).

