7.3.3. Clinical Measures

- Vital Signs and Respiratory Status:
 - Temperature, heart rate, systolic and diastolic blood pressure and respiration rate will be assessed three times daily during hospitalization between approximately 8 AM to 8 PM. Three times daily assessments should be made at approximately the same time each day, morning, afternoon and evening, and at least 5 hours apart. Measurements will be made once at clinic visits post-discharge.
 - The following evaluations will be recorded for respiratory status: Oxygen saturation (by transcutaneous oximetry), modality and quantity of oxygen administration; duration of oxygen supplementation and method of support, with dates and times will be recorded for invasive methods such as BiPAP, CPAP (i.e. new use in the hospital for respiratory distress and not for chronic use such as for sleep apnea), and mechanical ventilation; and for non-invasive methods such as nasal canula, facetent facemask etc. Respiratory status will be assessed

three times daily during hospitalization between approximately 8 AM to 8 PM, and once daily at clinic visits post-discharge. Three times daily assessments should be made at approximately the same time each day, morning, afternoon and evening, and at least 5 hours apart.

- Influenza symptoms: The presence and severity of influenza symptoms (nasal symptoms (rhinorrhea, congestion), feverishness, cough, myalgias, fatigue, diarrhea, dyspnea, headache, sore throat, nausea and vomiting) will be recorded once daily during hospitalization. The investigator or designee will assess and record influenza symptoms based on interview with the subject at approximately the same time each day. In situations when subjects may not be able to communicate their symptoms, for example in subjects ventilated and/or sedated, the investigator or designee will record those signs/symptoms as 'unable to assess'.
- Development of septic shock will be assessed by occurrence of hypotension requiring vasopressive therapy and serum lactate level >2 mM after adequate fluid resuscitation [Shankar-Hari, 2016; Seymour, 2016; Singer, 2016]. Additional information will be provided in the SRM.
- The number of days in the hospital, date and time of ICU admission and discharge, if applicable, and date and time of hospital discharge will also be recorded.

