The clinical response based on vital signs/ventilation status requires 24-hour confirmation. Considering 2-hour assessment window, the response confirmation period is 22 hours, i.e. all assessments within 22 hours of the initial response and at least one at or beyond 22 hours need to meet the criteria in order for the response to be confirmed. Any missing scheduled assessment will be imputed with response value of 0 (1 means response). Only hospital discharge due to clinical response or a confirmed response based on vital signs/ventilation criteria is considered as event for the TTCR analysis. Hospital discharge due to clinical improvement can serve as 24-hour confirmation for the clinical response and the event date should be the onset of the vital signs response. Subjects who died prior to achieving a clinical response will be assigned a worst value of TTCR (99 days). All other subjects who did not achieve a confirmed response will be censored at the last assessment date of vital signs.

For further details of the calculation of TTCR see Section 11.6.4.

Model Specification

Not applicable

Model Checking & Diagnostics

Not applicable

Model Results Presentation

Not applicable

Sensitivity and Supportive Statistical Analyses

 No sensitivity analyses or subgroup analyses will be performed given the small number of subjects.

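### Read literally, the SAP's 24-hour confirmation rule lets any later qualifying reading override a failed or missing 24-hour reading, so TTCR can be dated to a response that did not last 24 hours

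*SAP*

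**What the plan says.** Protocol 7.3.1 defines clinical response as resolution of the signs "within the respective resolution criteria, maintained for at least 24 hours, or hospital discharge, whichever comes first". SAP 7.1.2 repeats the requirement: "The clinical response based on vital signs/ventilation status requires 24-hour confirmation". It then allows for timing: "Considering 2-hour assessment window, the response confirmation period is 22 hours". The operative rule follows as an explanation of that sentence: "all assessments within 22 hours of the initial response and at least one at or beyond 22 hours need to meet the criteria". A confirmed event is dated at the initial response.

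Three other provisions bear on the rule:

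- **Missing readings (SAP 7.1.2).** "Any missing scheduled assessment will be imputed with response value of 0 (1 means response").
- **Schedule (Protocol 7.3.3).** "Three times daily assessments should be made at approximately the same time each day, morning, afternoon and evening, and at least 5 hours apart". SAP 11.6.4 supplies 08:00, 14:00 and 20:00 when a clock time is missing.
- **Discharge (SAP 7.1.2 and 11.6.4).** Discharge for clinical improvement during the 24-hour confirmation period serves as confirmation, and the event keeps the date of the vital-signs onset.

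**The concern.** The rule has two tests. The first covers readings up to 22 hours after onset. The second needs one qualifying reading at or beyond 22 hours. It sets no upper time limit, does not ask for the first such reading, and does not ask the readings in between to qualify.

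With three daytime readings at fixed hours, the reading that decides whether a response lasted 24 hours falls 24 hours after onset, outside the first test. Failing it breaks neither test if any later reading qualifies. A response seen to last 12 to 18 hours and then lost can be recorded as a confirmed 24-hour response at its onset.

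The event and its date enter the primary results: the Kaplan-Meier median and responder proportion per arm (SAP Table 4), the individual TTCR figure (Figure 2.1) and the plots of biomarker AUC against TTCR (Figures 6.2, 6.4, 6.6 and 6.8).

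**Working it through.** **Inputs.** Required duration 24 h (Protocol 7.3.1; SAP 7.1.2). Assessment window 2 h (SAP 7.1.2). Reading times 08:00, 14:00 and 20:00 (SAP 11.6.4, consistent with Protocol 7.3.3). Enrolled subjects 10, randomized 2:2:1 (SAP section 1).

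**The plan's own figure.** 24 h − 2 h = 22 h. It reproduces.

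**Where the readings fall, in hours after onset:**

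| Onset at | Readings inside 22 h | First reading at or beyond 22 h | Next reading |
|---|---|---|---|
| 08:00 | 0, 6, 12 | 24 | 30 |
| 14:00 | 0, 6, 18 | 24 | 30 |
| 20:00 | 0, 12, 18 | 24 | 36 |

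**Case 1: only the 24 h reading fails.**

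- *SAP text.* The first test passes. The second passes at 30, 30 or 36 h. TTCR is the initial onset.
- *First-reading rule* (every reading through the first at or beyond 22 h must qualify). The initial onset is rejected. Later starting points before 24 h are rejected too, because the failed reading lies inside their own 22 h. For an 08:00 onset, the starts at 6 h and 12 h meet the failure 18 h and 12 h later. The search restarts at 30, 30 or 36 h.
- *Difference.* 30/24 = 1.25 days (08:00 or 14:00 onset) or 36/24 = 1.5 days (20:00 onset).

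**Case 2: the relapse starts at 24 h and lasts D days, then recovery is sustained (08:00 onset).** The SAP text still returns the initial onset. The first-reading rule returns onset + (1 + D) days. For D = 1, 3, 7 and 14 this is 2, 4, 8 and 15 days later. Discharge for improvement is itself an event, so an earlier discharge of that kind would shorten the gap.

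**Case 3: relapse at 24 h, one isolated qualifying reading on day 7, none after.** The SAP text confirms a response at the initial onset. The first-reading rule gives no vital-signs response, so the responder count changes as well as the date.

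**Case 4: relapse at 24 h and the criteria are never met again.** Neither rule confirms a response.

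**Case 5: the 24 h reading is missing.** It is set to 0 and bypassed exactly as in Case 1. The conservative imputation has no force at the reading where it matters most.

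**All patterns over three days.** Nine readings give 2^9 = 512 patterns. The two rules differ in 79. In 75 of these only the SAP text scores a response within the three days; in the other 79 − 75 = 4 both score one, at different times. These are counts of patterns, not probabilities.

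**Does another provision close the gap?** SAP 11.6.4 deals with missing times, discharge, death and censoring, and does not name the confirming reading. SAP 11.3 says the study uses no assessment windows, so an upper limit such as 26 h cannot be inferred from elsewhere.

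**Weight of one subject.** If the 2:2:1 ratio held exactly, 10 subjects split 4, 4 and 2. One changed responder moves an arm's proportion by 1/4 = 25 points or 1/2 = 50 points, and the influenza-positive population may be smaller still.

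**The case against.** The strongest reply is that the clause explains the sentence before it. That sentence speaks of 24-hour confirmation with a 2-hour window, so the natural confirming reading is the one due at about 24 hours, allowed up to 2 hours early. That is probably what the authors meant. It does not remove the point: the text never says so, and a programmer who follows it will code something else.

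It can also be said that misdating would be visible, since TTCR and vital signs are listed by subject (Listings 31 and 33) and TTCR is plotted by subject. That is partly right. The summary table would still carry the wrong date, and SAP 7.1.2 plans no sensitivity analysis.

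Four stronger readings are tempting, and the documents do not support them:

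- **Every subject who relapses at 24 hours is scored a responder.** Not so. A later qualifying reading is needed (Case 4).
- **The error is large enough to rival a treatment effect.** Protocol Table 8 gives 1 day for HR 1.2 in less severe subjects, but that belongs to the 300-subject design, and a shift shared by all arms is not a treatment effect. The documents give no relapse rate. Simulations that assume a chance of 0.1 to 0.5 of meeting all criteria at a reading before stable recovery put the affected share anywhere from about 2% to 31%, so the assumption drives the answer. At the upper assumptions even the first-reading rule gives medians of 1.25 to 3.0 days, far from the plan's 5.8.
- **The rule dilutes the difference between arms.** SAP 2.1 and 2.4 make the analysis descriptive with no hypothesis test. The SAP synopsis and Table 4 plan TTCR medians and proportions per arm only. The one mention of a median difference is a footnote to the TTRR row of Table 5.
- **Two clinic readings weeks apart can confirm a response in a subject discharged for another reason.** Protocol 7.3.1 counts any discharge as a response. That case arises because the SAP narrows discharge to clinical improvement, which is a separate matter.

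**Conclusion.** The concern holds in a limited form. As written, SAP 7.1.2 can confirm a response that does not meet the 24-hour requirement of Protocol 7.3.1, and can date the event at its onset. This requires a failed or missing 24-hour reading followed by at least one qualifying reading.

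The error is 1.25 to 1.5 days when only the 24-hour reading fails, and grows with the length of the relapse. These figures assume the nominal reading times and no discharge for improvement in between. The frequency is unknown, and no effect on a treatment comparison is claimed. With 10 subjects, what is at stake is an accurate description: one event can move an arm's median, responder proportion or individual plot. Because this is the rule for the primary endpoint, it should be corrected rather than left to the programmer's interpretation.

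**What to change.** Replace the confirmation clause in SAP 7.1.2 with wording such as:

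*Every assessment from the initial response up to and including the first scheduled assessment 22 hours or more after it must meet the criteria; a missing scheduled assessment counts as not met. Otherwise the response is not confirmed, and the search restarts at the next assessment that meets the criteria.*

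Keep the present exception that discharge for clinical improvement during the confirmation period serves as confirmation. Without it, a subject discharged as improved before 22 hours would have no inpatient reading that could confirm the response, and the new sentence would contradict SAP 7.1.2 and 11.6.4. A rule limited to inpatient readings, or a fixed cap such as 36 hours, is not needed to close the gap.

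The cost is one sentence and a small change to the derivation code, made before unblinding, when the SAP says its final-analysis decisions are taken. TTCR will be later for some subjects, and a subject with only an isolated later qualifying reading may no longer count as a vital-signs responder.
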